13.4.6 Descriptive Analyses

The log₂ antibody titers of each group at each time point will be summarized and presented using histograms and strip charts for visual comparison. AE rates in each group will be summarized by tabulation.

13.5 Interim Analyses

Not applicable.

13.6 Statistical Hypotheses

We hypothesize that certain molecular signatures (immune markers, expression of genes, miRNAs, and metabolites), are associated to, and can predict the innate and adaptive immune response to the vaccine.

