approaches offer a new approach to describe the global architecture of the immune response to Shingrix®. Systems biology is a biology-based interdisciplinary study field that focuses on complex interactions in biological systems, using a new holistic perspective. Systems biology offers several so-called “Omic” technologies that can provide unbiased and rich information on the physiological state of organisms through their molecular profiles. These systems biological approaches are likely to be of value in identifying molecular signatures that are induced rapidly after vaccination and that correlate with, and predict, the later development of protective immune responses. Furthermore, the predictive signatures would highlight new correlates of protective immunity and stimulate the formulation and validation of new hypotheses on the biological mechanisms by which innate immune responses modulate vaccine-induced immunity and protection.¹⁵ This information would be useful in better understanding this new vaccine and compare it to the previous one. Accordingly, a key goal of the present proposal is to identify molecular signatures that predict the immune response to vaccination with Shingrix® in people above 50 years of age, and to obtain greater mechanistic insight underlying age-related immunological defects if they exist.

In summary, the proposed study offers an unprecedented opportunity to capture the global architecture of immune responses to Shingrix® in two age groups: those between the ages of 50 and 60, and those who are 70 years of age and above. This is likely to have a major impact in three areas: (i) the elucidation of molecular signatures or biomarkers that predict vaccine immunogenicity or efficacy and will thus be relevant from a public health perspective. (ii) such molecular signatures may illuminate the molecular defects responsible for potential sub-optimal immunity in the elderly population. (iii) will help compare the immune responses to vaccination with the two available HZ vaccines, Shingrix® and Zostavax®, since a similar study using systems biology was done previously by our group on Zostavax® vaccine.¹⁶

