2.1. Hypotheses

The efficacy of the recombinant, adjuvanted herpes zoster vaccine (Shingrix®) is high. We hypothesize that early innate signatures of vaccination should correlate with responses to, and predict the immunogenicity of, Shingrix® in older adults, independently of age.

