13.4 Analysis Plan

Data from the study will be analyzed using the statistical software R. High-throughput data will be analyzed using appropriate methods, either by stand-alone software or modules in leading statistical software, e.g. the Bioconductor in the R framework. For cytokine data, missing values will be dealt with using multiple imputations. For gene expression and metabolomics data, nearest neighbor method and local least squares may be used to fill missing values. Unsupervised learning techniques such as PCA, PLSDA, clustering, and factor analysis will be used for the visualization and identification of global patterns. For descriptive endpoints, we will generate summary statistics, and visualize the data using histograms and boxplots when applicable. For the identification of innate signatures, the two age groups will be analyzed separately.

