13.4.5 Analyses of Exploratory Endpoint(s)/Outcome(s)

Exploratory Endpoint 1. The innate immune response signatures are identified from traditional immune parameters, gene expression measured by RNA-seq experiment, and metabolomics data measured by LC/MS. The innate signatures will be identified for the two age groups separately. The traditional immune parameters, genes, and metabolites that change significantly over baseline after immunization are considered innate signatures.

Traditional markers will be tested using paired t-test or Wilcoxon test against D0, and significant markers will be considered part of the innate immune signature.

RNA-seq data will be preprocessed using Bowtie and Tophat, and FPKM (fragments per kilobase of exon model per million mapped reads) values will be calculated. Gene level comparison of D1, D4, D14 and D30 vs D0 will be conducted using DESeq to find the transcriptomics signature of vaccination.

Metabolomics data will be processed using packages apLCMS, XCMS, and xMSAnalyzer and generate data tables containing accurate mass m/z , retention time(s), intensity, coefficient of variation, and

related descriptive characteristics, including minimal information standards for metabolomics data. SAM(8) and similar methods will be used to detect differential abundance of features between D1, D4, D14 and D30 vs D0 to select metabolic innate signatures.

After each vaccination, the innate signatures that are correlated with the D30 antibody titers are considered correlation signatures of the innate immune responses. The correlation will be assessed using Spearman's correlation and the associated p-values.

Exploratory Endpoint 2. We will use paired t-test or Wilcoxon test to compare each immune parameter (changes in phenotype of T cell responses and the kinetics of these changes) between D7, D14 and D30 after vaccination and D0 for each dose of Zoster vaccine.

Exploratory Endpoint 3. We will use paired t-test or Wilcoxon test to compare each immune parameter (changes in the magnitude of activated B cells, antibody secreting cells and memory B cells and the kinetics of these changes) between D7, D14 and D30 after vaccination and D0 for each dose of Zoster vaccine.

Exploratory Endpoint 4. We will use paired t-test or Wilcoxon test to compare VZV serology between D14, D30, D180 and D270+ (optional visit) after vaccination and D0 for each dose of Zoster vaccine.

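### The hypotheses say innate signatures predict the response, independently of age, but the only prespecified link to a later response is a correlation, which can support association only

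*Combined protocol and SAP*

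**What the plan says.** Three places in the combined protocol and SAP set prediction as an aim.

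- Section 1.1 calls it a key goal to "identify molecular signatures that predict the immune response to vaccination with Shingrix® in people above 50 years of age".
- Section 2.1 hypothesizes that early innate signatures correlate with responses and "predict the immunogenicity of, Shingrix® in older adults, independently of age".
- Section 13.6 states that signatures "are associated to, and can predict the innate and adaptive immune response to the vaccine". It does not mention age.

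The analysis that relates signatures to a later response is under Exploratory Endpoint 1 in section 13.4.5. Features that change significantly from baseline form the innate signature. After each vaccination, "the innate signatures that are correlated with the D30 antibody titers are considered correlation signatures of the innate immune responses". The method is given in one sentence: "The correlation will be assessed using Spearman's correlation and the associated p-values".

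On age, section 13.4 says "For the identification of innate signatures, the two age groups will be analyzed separately", and section 13.4.5 repeats it: "The innate signatures will be identified for the two age groups separately". Section 13.7 powers the correlation on 30 samples. It also says that false discovery rate will be used in the actual analysis, in a paragraph about gene expression. The end of section 13.4.5 allows other approaches ad hoc and names gene set enrichment as an example.

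**The concern.** A correlation computed in the same people in whom the feature was picked describes those people. Prediction is a statement about people not used in the picking, and nothing in the plan measures that. No prediction model, hold-out set, cross-validation or accuracy measure is specified. PCA, PLSDA, clustering and factor analysis are named in section 13.4 for visualization and global patterns only.

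Independence from age has no test either. There is no pooled model with age, no signature-by-cohort interaction, and no application of one cohort's signature to the other. Finding a correlation significant in each cohort separately, or in one and not the other, does not show whether the relation depends on age.

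The correlation also targets antibody titers alone, so prediction of the T-cell and B-cell parts of the adaptive response has no specified analysis.

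At stake is what the trial may say about its own hypothesis. As planned, it can report associations, and two parts of the hypothesis would stay untested.

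**Working it through.** **1. The plan's own figure.** Inputs from section 13.7: n = 30, two-sided alpha 0.01, Pearson r = 0.57, stated power 80%. By Fisher z, power = Φ(atanh(r)·√(n−3) − z(1−α/2)) = Φ(0.6475 × 5.196 − 2.576) = Φ(0.789) = 78.5%. A t-based version with bias correction gives 79.2% and a simulation 79.5%. The figure reproduces. For the Spearman test actually planned (variance factor 1.06), power is about Φ(3.268 − 2.576) = 75.6%. The arithmetic is therefore not the problem.

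**2. Hypothesis against analysis.**

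| Part of the hypothesis | Prespecified analysis |
|---|---|
| Associated with response | Spearman correlation with D30 titer (13.4.5) |
| Predicts response | None |
| Independently of age (2.1 only) | None |

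That the correlation runs within each cohort is an inference. The correlation sentence does not say so, but signatures are identified separately by age (13.4, 13.4.5) and the power statement uses 30, one cohort's size (13.7).

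**3. Optimism of an in-sample correlation.** Suppose m features unrelated to the titer are screened in 30 people, and assume they are independent. The largest of m null p-values' correlations has its median where the single-test p-value is p = 1 − 0.5^(1/m), and |r| = t/√(t² + 28) with t the two-sided critical value on 28 degrees of freedom. For m = 100: p = 0.0069, t = 2.916, |r| = 2.916/√(8.503 + 28) = 0.48. Simulated Spearman medians agree closely:

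| Features screened | t formula | Simulated median |
|---|---|---|
| 50 | 0.44 | about 0.45 |
| 100 | 0.48 | about 0.49 |
| 1,000 | 0.58 | about 0.59 |
| 20,000 | 0.68 | about 0.70 |

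Section 13.7 gives fewer than 50 immune parameters, about 20,000 genes, and more than 100 truly changing genes with no upper limit. The number entering the correlation step is therefore unknown. The 20,000 row ignores the filter on change from D0 and is an upper bound. Correlated genes behave like fewer features.

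**4. Why in-sample fit does not measure prediction.** In the same null setting, a score averaging the 10 best features has a median in-sample correlation of 0.79, 0.88 and 0.93 for 100, 1,000 and 20,000 features. Frozen and applied to 30 new null subjects, its median correlation is about 0.

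**5. What the design can say about age.** Compare two independent correlations, 30 people each, with SE = √(2/27) = 0.272 on the Fisher z scale and two-sided alpha 0.05. Taking 0.57 in one cohort and an assumed value in the other:

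- against 0: Φ(0.6475/0.272 − 1.96) = 66%
- against 0.2: Φ(0.4448/0.272 − 1.96) = 37%
- against 0.3: Φ(0.3380/0.272 − 1.96) = 24%

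A non-significant interaction would thus be weak evidence of independence from age, so the confidence interval is what should be read. A pooled analysis of all 60, adjusted for age, at alpha 0.01 would detect a common r of about 0.43 with 80% power.

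**The case against.** The strongest reply is that the analysis section is already modest. It calls its results correlation signatures, and the matching objective in section 2.4 speaks of correlation with adaptive responses. A reader might infer that a chance correlation would be reported as a predictive signature. The documents do not say that: no objective or analysis labels a feature predictive. This part of the reply stands.

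A reader might also take the 20,000-feature value of 0.70 as what the plan would produce, and note that it exceeds 0.57. That does not follow either. Features are first filtered on change from D0, without using the titer. The 0.57 is a true correlation detectable in one test, not a reporting threshold. False discovery rate control, if applied, would stop most such calls: with Benjamini-Hochberg at an assumed 5%, the first cut is |r| of about 0.60 for 100 features and 0.74 for 20,000, and about 86% to 95% of simulated null datasets gave no call. This stands in part. Section 13.7 does not say that its commitment covers the correlation step, for which section 13.4.5 cites only p-values. Control of false calls also gives no out-of-sample performance.

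The clause allowing ad hoc methods leaves room for validation but commits to none. Finally, the analysis is exploratory and touches neither the primary comparison nor safety. That limits the weight of the point without removing the mismatch.

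**Conclusion.** The mismatch holds. Sections 2.1 and 13.6 hypothesize prediction, section 2.1 adds independence from age, and the only prespecified analysis addresses association with D30 antibody titers. The optimism in an in-sample correlation ranges from a median null maximum of about 0.45 (50 features) to at most about 0.70 (20,000, unfiltered), depending on a feature count the plan does not give. These figures assume no true signal, n = 30 and independent features, and they omit the D0 filter and any false discovery rate control. That the correlation is within cohort is inferred. Severity is low, because the endpoint is exploratory. The point is a gap in the plan; the stated power figure is correct.

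**What to change.** Amend section 13.4.5 as follows.

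1. For any signature claimed to predict, report cross-validated performance within each cohort, repeating both the change-from-D0 filter and the correlation-based selection inside each fold.
2. For independence from age, fit a pooled model of all 60 with age cohort and a signature-by-cohort interaction, and report the interaction with its confidence interval. Report transfer of a frozen score between cohorts as supportive only. It should not be the sole criterion, because failed transfer may reflect a real age difference as well as overfitting.
3. State that false discovery rate control applies to the correlation step.
4. Use the word predict only for signatures supported by item 1. Otherwise limit sections 2.1 and 13.6 to association, which is an acceptable remedy in itself.

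The cost is a little more analysis and no new data. Performance estimates will be less favourable and imprecise at 30 per cohort, and power to detect a difference between cohorts will be low (24% to 66% in the cases above).

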13.7 Sample Size Considerations

For sample size consideration, we will use the alpha level of 0.01 for the immune parameters. Given less than 50 immune parameters will be tested, this alpha level translates to an expected count of false positives of <1, which is an acceptable level. For the gene expression data and for sample size consideration only, we will use the alpha level of 0.0005 to offset the effect of multiple testing. This means an average of one false positive for every 2000 null genes tested; given ~20,000 genes will be measured, this alpha level translates to an expected 10 false positives. We expect >100 genes will be truly differentially expressed. Thus among all genes called differentially expressed, the proportion of false positives will be <10%, which is an acceptable level in gene expression studies. We note this consideration is for sample size analysis alone. In actual data analysis false discovery rate (FDR) will be used.

For the traditional immune parameters, with 30 samples in a treatment group, we can reject the null hypothesis of equal means with 80% power if the true effect size (mean difference/sigma) is 0.66, using a two-sided paired t-test and the alpha level of 0.01. For the gene expression, the actual data analysis will be performed using the false discovery rate. For simplicity, for sample size consideration, we will consider the simpler case of a paired t-test. With 30 samples in a treatment group, we can reject the null hypothesis of equal means with 80% power if the true effect size (mean difference/sigma) is 0.88, using a two-sided paired t-test and the alpha level of 0.0005.

For unpaired test, with sample size of 30 per group, at the alpha level of 0.01, we can reject the null hypothesis of equal means with 80% power if the true effect size ((mean0-mean1)/sigma, assuming equal variance) is 0.91 using an unpaired two-sided t-test.

For a paired t-test, with the sample size of 30, at the alpha level of 0.01, we can reject the null hypothesis of no change with 80% power if the true effect size (mean difference/sigma) is 0.66.

For correlation analysis, with 30 samples in the treatment group, at the alpha level of 0.01, we can reject the null hypothesis of zero correlation with 80% power if the true correlation is 0.57 using a two-sided test for Pearson's correlation coefficient.

14. Identification and Access to Source Data

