13.2 Endpoints

Primary Endpoint

- Differences in innate immune signatures between D0, D1, and D7 and each dose of Zoster vaccine recombinant, adjuvanted, in both age cohorts.

Secondary Endpoint

- Differences in related adverse events and serious adverse events between each dose of Zoster vaccine recombinant, adjuvanted, in both age cohorts.

Exploratory Endpoints

- The changes in transcriptomics, metabolomics and immune cell populations between D0 (before vaccination) and D1, D3, D7, D14 and D30 after each dose of Zoster vaccine recombinant, adjuvanted, in both age groups
- The changes in the phenotype of T cell responses and the kinetics of these changes between D0 (before vaccination) and D7, D14 and D30 after each dose of Zoster vaccine recombinant, adjuvanted, as well as D180 and D270+ (optional visit) in both age groups.
- The changes in the magnitude of activated B cells, antibody secreting cells and memory B cells and the kinetics of these changes between D0 (before vaccination) and D7, D14 and D30 after each dose of Zoster vaccine recombinant, adjuvanted, as well as D180 and D270+ (optional visit) in both age groups.
- The changes in VZV serology between D0 (before vaccination) and D14 and D30 after each dose of Zoster vaccine recombinant, adjuvanted, as well as D180 and D270+ (optional visit) in both age groups.
- The changes in specificity, magnitude and phenotype of VZV-specific (gE and other antigens) T cells and the kinetics of these changes between D0 (before vaccination) and 7, 14, 30 days after each dose of Zoster vaccine recombinant, adjuvanted, and at D180 and D270+ (optional visit) in both age groups.
- The changes in magnitude of VZV-specific B cells and the kinetics of these changes between D0 (before vaccination) and 7, 14, 30 days after each dose of Zoster vaccine recombinant, adjuvanted, and at D180 and D270+ (optional visit) in both age groups.
- Baseline stool microbiome alpha and beta diversity parameters.

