13.4.2 Primary Analysis of Primary Endpoint

We will use paired t-test or Wilcoxon signed-rank test to compare each immune parameter (innate immune responses) between D1 and D7 after first dose of vaccine, between D61 and D67 after second dose of vaccine, and D0 and D60 (at each dose of Zoster vaccine). The choice of the test will depend on the normality of the data, as judged by normal Q-Q plots.

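### Section 13.7's expected false-positive count of below 1 is a one-test-per-parameter figure, not the error level of the primary analysis, and its correlation power is for Pearson although the plan tests Spearman

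*Combined protocol and SAP*

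**What the plan says.** Section 13.7 sets alpha at 0.01 for the immune parameters for sample-size purposes, states "Given less than 50 immune parameters will be tested, this alpha level translates to an expected count of false positives of <1", and calls that level acceptable. After discussing gene expression, the same paragraph ends: "In actual data analysis false discovery rate (FDR) will be used". The next paragraph returns to the subject with "For the gene expression, the actual data analysis will be performed using the false discovery rate", and says nothing equivalent for the traditional immune parameters.

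The primary analysis in 13.4.2 compares each innate immune parameter by paired t-test or Wilcoxon signed-rank test "between D1 and D7 after first dose of vaccine, between D61 and D67 after second dose of vaccine, and D0 and D60". The primary endpoint in 13.2 reads "Differences in innate immune signatures between D0, D1, and D7 and each dose of Zoster vaccine", in both cohorts. Section 13.4 adds: "For the identification of innate signatures, the two age groups will be analyzed separately". Section 13.4.2 gives no alpha and no adjustment.

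Under Exploratory Endpoint 1 in 13.4.5, traditional markers are tested against D0 and "significant markers will be considered part of the innate immune signature". Signatures are then related to D30 antibody titers: "The correlation will be assessed using Spearman's correlation and the associated p-values". The matching power statement in 13.7 (n = 30, alpha 0.01, 80% power at a correlation of 0.57) is for Pearson's coefficient.

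**The concern.** The argument in 13.7 multiplies the number of parameters by alpha, as though each parameter were tested once. The plan tests each parameter several times per cohort, in two cohorts. A reader who takes the count as the false-positive level of the primary analysis would be too reassured, unless FDR control covers these tests. The sections that govern the analysis do not say that it does. The point has consequences because 13.4.5 admits every traditional marker significant against D0 to the innate signature without defining significant, so unadjusted false positives in those tests would enter it.

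The correlation figure has a similar gap between planning and analysis. The study's hypothesis is that early signatures predict immunogenicity, and the power quoted for that question belongs to a different test from the one planned.

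**Working it through.** **1. The plan's own count.** Inputs from 13.7: fewer than 50 parameters, so at most 49; alpha 0.01.

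Expected false positives = null parameters × tests per parameter × alpha = 49 × 1 × 0.01 = 0.49. The stated figure is reproduced. One contrast in both cohorts would still just fit: 49 × 2 × 0.01 = 0.98.

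**2. Contrasts per parameter.** Section 13.4.2 supports two readings:
- Literal, three contrasts: D1 v D7, D61 v D67, D0 v D60.
- Read with the endpoint in 13.2, four contrasts: D1 and D7 each v D0; D61 and D67 each v D60.

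There are two cohorts, analysed separately (13.4).

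**3. Count over the primary contrasts.** Expected false positives = null parameters × contrasts × cohorts × 0.01.

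| Null parameters | Contrasts | One cohort | Both cohorts |
|---|---|---|---|
| 49 | 3 | 1.47 | 2.94 |
| 49 | 4 | 1.96 | 3.92 |
| 20 | 3 | 0.60 | 1.20 |
| 20 | 4 | 0.80 | 1.60 |

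The largest numbers of null parameters that keep the count below 1 are:
- One cohort: 33 with three contrasts (33 × 3 × 0.01 = 0.99), or 24 with four (0.96).
- Both cohorts: 16 with three contrasts (16 × 6 × 0.01 = 0.96), or 12 with four (12 × 8 × 0.01 = 0.96).

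Correlation between markers does not alter an expected count.

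**4. The plan's correlation power.** Inputs from 13.7: n = 30, two-sided alpha 0.01, Pearson r = 0.57. By Fisher's z with the small-sample bias term:

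z = [arctanh(0.57) + 0.57/(2 × 29)] × √27 − 2.576 = (0.6475 + 0.0098) × 5.196 − 2.576 = 0.84, so power is about 80%.

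Simulation (200,000 samples) gives just under 80%. The stated figure is reproduced for Pearson.

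**5. The same for Spearman.** Simulation with 200,000 samples per setting, n = 30, two-sided 0.01, t approximation. Bivariate normality is my assumption; the documents do not state it. Under it, the Spearman coefficient equals (6/π) × arcsin(r/2).

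| Underlying Pearson r | Spearman coefficient | Spearman power |
|---|---|---|
| 0.57 | 0.55 | about 72% |
| 0.588 | 0.57 | about 76% |
| 0.605 | 0.59 | about 80% |

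**6. Sensitivity to normality.** With lognormal margins (log-scale SD 1, an assumption) and a true Pearson correlation of 0.57, Pearson power is about 77% and Spearman power about 93%. The direction of the difference therefore depends on the shape of the data.

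**The case against.** The best defence is that 13.7 contains no arithmetic error. It counts per comparison throughout: the gene-expression figure, 20,000 × 0.0005 = 10, also takes one test per gene. It says that its alpha levels are for sample size, and that FDR will be used in the actual analysis. No analysis section says the immune parameters will be tested at a fixed 0.01. If FDR applies to them, a raw count does not describe the final analysis. The bound also stacks assumptions, since the fewer than 50 parameters may include adaptive measures, and parameters that truly change cannot give false positives.

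Most of this stands, and it rules out some tempting inferences. A reader might infer that the primary analysis will yield three or four false positives; the documents support that only as an upper bound, with 49 innate parameters, all null, and no adjustment. A reader might also infer that the plan has no multiplicity control for the immune parameters. The closing sentence on FDR is general enough to cover them, so the fair statement is that coverage is unclear.

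What does not fall is the mismatch itself. The count is the stated reason for accepting alpha 0.01, on which the 0.66, 0.91 and 0.57 effect sizes rest, yet the primary analysis is not one test per parameter on either reading. Even if FDR is meant throughout, no family or q level is given.

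On the correlation, 13.7 openly labels its figure Pearson, the analysis is exploratory, and Spearman can have the higher power with skewed data.

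**Conclusion.** The point holds as a mismatch between the planning figures and the planned tests. The count of below 1 is correct per contrast and per cohort (at most 0.49), but should not be read as the error level of the whole primary analysis. Unadjusted, that level is at most 1.47 or 1.96 per cohort and 2.94 or 3.92 overall, with proportionately lower values for fewer null parameters. Whether FDR control replaces these figures cannot be settled from the text.

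The 80% power at 0.57 is right for Pearson. For Spearman under bivariate normality it is about 72% if 0.57 is the underlying Pearson correlation, or about 76% if 0.57 is the Spearman coefficient itself. An unconditional claim that the correlation analysis is underpowered relative to the plan would go too far, because the documents say nothing about the distribution of markers or titers.

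Both figures should be restated. The FDR element is mainly a request for clarification.

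**What to change.** - **13.7, count.** Replace the figure of below 1 with: at most about 0.5 per contrast per cohort at unadjusted alpha 0.01; the total is null parameters × contrasts × cohorts × 0.01 (up to 2.9 or 3.9 if all of up to 49 parameters are innate and null), before FDR control.
- **13.4.2.** List the primary contrasts one by one, so that three or four is settled.
- **13.4.2 and 13.4.5.** State that FDR control applies to the immune-parameter tests and to the Spearman p-values, with the family and q level chosen by the sponsor. Benjamini-Hochberg within each cohort is one defensible choice among several.
- **13.7, correlation.** Restate as: Spearman, single marker, n = 30, two-sided alpha 0.01, 80% power at an underlying Pearson r of about 0.605 (Spearman about 0.59), assuming bivariate normality.

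The cost is wording, slightly less favourable stated figures, and some power under FDR when few markers change. In simulation (4,000 trials, independent tests, 147 or 196 tests per cohort, effect size 0.66 for every true change), Benjamini-Hochberg at q = 0.05 gave about 67% power when 10% of tests were true changes and about 80% when 25% were, against about 80% at fixed alpha 0.01. At q = 0.10 the figures were about 78% and 89%. FDR limits the expected proportion of false calls rather than their number, so a count below 1 should not be presented as its result.
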